## 5 INTRODUCTION

### 5.1 Background

Cystic fibrosis (CF) is an autosomal recessive disease with serious, chronically debilitating morbidities and high premature mortality and at present, there is no cure. CF affects approximately 70,000 individuals worldwide. Based on the size of the population, CF qualifies as an orphan disease. Despite progress in the treatment of CF with antibiotics and mucolytics, the predicted median age of survival for a person with CF is approximately 40 years.

CF is caused by reduced quantity and/or function of the cystic fibrosis transmembrane conductance regulator (CFTR) protein due to mutations in the *CFTR* gene. The CFTR protein is an epithelial chloride channel that aids in regulating salt and water absorption and secretion and pH balance in multiple organs, including the lungs, pancreas and other gastrointestinal organs, and sweat glands. In people with CF, decreased CFTR chloride transport results in multisystem pathology. Although the disease affects multiple organs, progressive loss of lung function is the leading cause of mortality.

More than 2000 mutations in the *CFTR* gene have been identified. Based on the understanding of the molecular defects caused by *CFTR* mutations, 2 complementary approaches have been developed to address the decreased quantity and/or function of CFTR in order to enhance chloride transport in patients with CF. The first approach is to increase the quantity of CFTR delivered to the cell surface using small molecules known as CFTR correctors. The second approach is to increase the channel gating activity of CFTR at the cell surface using small molecules known as CFTR potentiators. One or both of these mechanisms may be necessary depending on the specific mutation. Because the channel gating activity of CFTR delivered to the cell surface by CFTR correctors can be enhanced by CFTR potentiators, together, CFTR correctors and potentiators provide complementary therapeutic approaches to improve chloride transport.

Lumacaftor (LUM) is a CFTR corrector, and ivacaftor (IVA) is a CFTR potentiator. LUM/IVA combination therapy is approved in the US, European Union, Canada, Australia, and Switzerland for the treatment of CF in patients 12 years of age and older who are homozygous for the F508del mutation, the most common mutation of the *CFTR* gene.

### 5.2 Study Rationale

CF is a chronic disease with challenges in long-term disease management. Inadequate treatment adherence is one of the most significant challenges in achieving effective health outcomes. An estimated 30-50% of medicines are not taken as recommended and adherence tends to decline after the first 6 months of treatment.

Effective disease management relies on consistent adherence habits, yet adherence is an invisible, and often an unmonitored, expectation in routine care. Discrepancies in clinical studies between objective (e.g., pharmacy refills) and self-reported measures of adherence (e.g., surveys, questionnaires) have led to development of smart adherence technology interventions (e.g., smart pill bottles). This study is designed to evaluate the impact of smart adherence technologies for supporting and monitoring LUM/IVA adherence rates among subjects 16 years of age and older with CF who are homozygous for *F508del*.

## 6 STUDY OBJECTIVES

### 6.1 Primary Objective

To evaluate the impact of smart adherence technologies for monitoring of LUM/IVA adherence rates among subjects 16 years of age and older with CF who are homozygous for the *F508del-CFTR* mutation

### 6.2 Secondary Objective

To collect subject and physician feedback on the use of smart adherence technology to monitor LUM/IVA adherence

## 7 STUDY ENDPOINTS

### 7.1 Primary Endpoint

Mean percentage adherence to LUM/IVA treatment over 48 weeks

### 7.2 Secondary Endpoints

- Mean percentage adherence to LUM/IVA treatment over 24 weeks
- Mean percentage adherence to LUM/IVA treatment from Week 25 through Week 48
- Proportion of subjects with  $\geq 80\%$  LUM/IVA adherence over 24 weeks
- Proportion of subjects with  $\geq 80\%$  LUM/IVA adherence over 48 weeks
- Proportion of subjects with  $\geq 80\%$  LUM/IVA adherence from Week 25 through Week 48
- Proportion of subjects with a non-physician-directed LUM/IVA interruption  $\geq 72$  hours over 48 weeks
- Number of non-physician-directed LUM/IVA interruptions  $\geq 72$  hours over 48 weeks
- Time to the first non-physician-directed LUM/IVA interruption  $\geq 72$  hours over 48 weeks

[REDACTED]

[REDACTED]

[REDACTED]

[REDACTED]

[REDACTED]

## 8 STUDY DESIGN

### 8.1 Overview of Study Design

This is a Phase 4, open-label, randomized, multicenter, 2-arm, parallel-group pilot study evaluating LUM/IVA adherence. Each study arm will use a smart technology with either active or inactive dosing alert and feedback features.

This study includes:

- Screening Period (Day -28 through Day -1)
- Treatment Period (Day 1 through Week 48)
- Safety Follow-up Visit (28 [ $\pm$  7] days after the final dose of LUM/IVA). Subjects who begin commercially available LUM/IVA combination therapy do not have to complete the Safety Follow-up Visit.

**Figure 8-1** depicts a schematic of the study design. Approximately 75 subjects will be enrolled in this study. All subjects will receive LUM 400 mg/IVA 250 mg every 12 hours (q12h) through Week 48.

[figure not shown]
Subjects will be stratified by age (<23 versus  $\geq$ 23 years of age) and forced expiratory volume in 1 second (FEV1) severity (<70% versus  $\geq$ 70% predicted) determined at the Screening Period and then randomized (2:1) to 1 of the 2 study arms:

- **Study Arm A:** Smart Pill Bottle, activated
- **Study Arm B:** Smart Pill Bottle (control), de-activated alerts and feedback features

Subjects will receive standardized education on the benefit of LUM/IVA, LUM/IVA adherence, and training on the use of the assigned smart adherence technology. During applicable study visits, subjects will complete adherence and technology satisfaction assessments. Physicians will also complete a technology satisfaction questionnaire. **Table 3-2** provides a list of assessments by study visit.

All subjects will be required to complete study assessments for all scheduled visits. Subjects who prematurely discontinue LUM/IVA will complete a Safety Follow-up Visit (see Section 8.1.3).

### Figure 8-1 Study Design

◆ Study Visit; ◆ Safety Follow-up Visit; IVA: ivacaftor; LUM: lumacaftor

Notes: The Safety Follow-up visit is only required for subjects who do not begin commercially available LUM/IVA within 28 ( $\pm$  7) days of the last dose of LUM/IVA.

### 8.1.1 Screening

Screening Visit assessments are listed in [Table 3-1](#).

Screening will occur within 28 days before administration of LUM/IVA. The investigator (or an appropriate authorized designee at the study site) will obtain informed consent or assent from each subject. If the time between screening and dosing exceeds 28 days as a result of unexpected operational delays (e.g., delayed drug shipment), then subjects do not require rescreening.

To prepare for study participation, subjects will be instructed on the study restrictions ([Section 9.3](#)).

Subjects previously screened for another Vertex study may participate in this study if they meet the eligibility criteria. Screening data from the previous study may be used for this study if they were obtained within 28 days before administration of LUM/IVA.

Subjects who do not meet the eligibility criteria may not be rescreened, with the following exceptions, all of which require medical monitor approval:

- Subjects who met all eligibility criteria but had an intercurrent illness (e.g., upper respiratory infection with fever) in the 5 days before the first LUM/IVA dose that was properly evaluated and which resolved fully
- Subjects who met all eligibility criteria but are not able to obtain required documentation within the allotted screening window
- Subjects who met all eligibility criteria but transiently (for personal reasons) are unable to commit to all study procedures
- Subjects who met all eligibility criteria but are not randomized for administrative reasons (e.g., interactive web response system is temporarily inaccessible or nonfunctional or LUM/IVA is not available at the study site)

Any subject granted approval by the medical monitor for any of the exceptions listed above may have the screening window extended by 1 week before needing to undergo any rescreening assessments. If more than 35 days have elapsed from screening before first dose of LUM/IVA, all screening assessments need to be repeated. Repetition of any screening assessment that did not meet eligibility criteria is not permitted, unless there is clear evidence of a laboratory error (e.g., hemolysis of sample). In all cases, the medical monitor must authorize retesting.

### 8.1.2 Treatment Period

Treatment Period visits and assessments are listed in [Table 3-2](#). Additional study visits may also occur as determined by the clinical site for routine care.

Subjects will be randomized at the Day 1 Visit to either Study Arm A or Study Arm B (described in [Table 8-1](#)). Each subject will be trained on the use of the assigned smart adherence technology and will use the technology throughout the Treatment Period. All subjects will receive LUM 400 mg/IVA 250 mg q12h throughout the Treatment Period.

Subjects who prematurely discontinue LUM/IVA treatment will complete a Safety Follow-up Visit (See [Section 8.1.3](#)).

**Table 8-1 Study VX15-809-114 Smart Adherence Technology Study Arms**

Smart Adherence Technology	Activated Features	Access to LUM/IVA Compliance Status	Number (n)
Smart Pill Bottle (Study Arm A)	Real-time dosing data transfer, electronic medication reminders/missed dose alerts (audio, visuals, texts, emails, phone calls)	Site staff and physicians, CRO, Vertex	50
Smart Pill Bottle, Control (Study Arm B)	Real-time dosing data transfer to CRO/Vertex only	CRO/Vertex only	25

CRO: contract research organization

The use of active smart adherence technologies (smart pill bottles) will provide subjects with objective and real-time feedback on dosing adherence, including reminders of upcoming or missed doses. Study physicians will access dosing adherence data and review them with subjects in Study Arm A at scheduled study visits. Subjects in Study Arm B will not receive any alerts, reminders, or real-time feedback on dosing adherence. Study Arm B will provide objective data on dosing adherence without influencing subjects to take a scheduled dose of LUM/IVA.

### 8.1.3 Follow-up

Subjects will have a Safety Follow-up Visit 28 ( $\pm$  7) days after the last dose of LUM/IVA. Safety Follow-up Visit assessments are listed in [Table 3-2](#). Subjects who begin commercial LUM/IVA before this visit do not have to complete the Safety Follow-up Visit.

### 8.1.4 Early Termination of Treatment

Subjects who prematurely discontinue LUM/IVA treatment for any reason (except withdrawal of consent or assent) and who do not begin commercial LUM/IVA will be asked to return to the clinical site 28 ( $\pm$  7) days of their last dose of LUM/IVA for a Safety Follow-up Visit.

Assessments performed at this visit will be the same for those in the Safety Follow-up Visit ([Table 3-2](#)).

If the subject withdraws consent or assent for the study, no further evaluations should be performed and no additional data should be collected. Vertex may retain and continue to use any data collected before such withdrawal of consent.

## 8.2 Rationale for Study Design and Study Drug Regimens

### 8.2.1 Study Design

This pilot study is designed to provide information about the effect of smart adherence technologies on LUM/IVA treatment adherence. An estimated 30-50% of medicines are not taken as recommended and adherence tends to decline after the first 6 months of treatment. Suboptimal adherence results in morbidity, mortality, preventable hospitalizations, a raised incidence of secondary complications, and therefore societal and economic burdens.

Effective disease management relies on consistent adherence habits, yet adherence is an invisible, and often an unmonitored, expectation in routine care. Discrepancies in clinical studies between objective (e.g., pharmacy refills) and self-reported measures of adherence (e.g., surveys, questionnaires) have led to development of smart adherence technology interventions

(e.g., smart pill bottles). These technologies allow patients to self-monitor medication adherence through real-time electronic feedback via visual and auditory alarms, texts, emails, phone calls, and online dashboards. Smart adherence technologies enhance adherence by offering a method for CF patients and physicians to objectively monitor medication compliance and to make long-term adherence both manageable and visible in daily routines.

This study is not designed or powered to assess a relationship between adherence and clinical outcomes. [REDACTED]

Subjects will be stratified by age (<23 versus  $\geq$ 23 years of age) and FEV1 severity (<70% versus  $\geq$ 70% predicted) determined at the Screening Period and then randomized (2:1) to 1 of the 2 study arms described in [Table 8-1](#).

A sample size of approximately 75 subjects is sufficient to detect a 5.6% difference between the study arms with 80% power.

## **8.2.2 Study Drug Dose and Duration**

### **LUM/IVA Dose Rationale**

Subjects will receive LUM 400 mg/IVA 250 mg q12h during the Treatment Period. This dose regimen has been approved in the US, European Union, Canada, and Australia for the treatment of CF in patients 12 years of age and older who are homozygous for the *F508del* mutation.

### **Study Duration Rationale**

Treatment adherence to approved medications tends to decline after 6 months. The 48-week study treatment duration was chosen to provide an adequate assessment of long-term adherence to LUM/IVA.

## **8.2.3 Rationale for Study Assessments**

The safety assessments are standard parameters for clinical studies in drug development and are generally recognized as reliable, accurate, and relevant to the study of patients with CF. All assessments with the exception of the patient- and physician-reported outcomes and use of smart adherence technologies were routinely measured in the LUM/IVA combination program.

Rationales for these assessments, the patient- and physician-reported outcomes, and use of smart adherence technologies are provided below.

### Spirometry

FEV1 as measured by spirometry is the most widely implemented standardized assessment to evaluate lung function in CF. This will be performed at the Screening Visit (See Section [11.5.5](#)).

### Ophthalmologic Examinations

Cases of noncongenital lens opacities have occurred in pediatric patients treated with ivacaftor, a component of LUM/IVA. Although other risk factors were present in some cases (such as corticosteroid use and exposure to radiation), a possible risk attributable to ivacaftor cannot be excluded. Baseline and follow-up ophthalmological examinations are recommended in pediatric patients initiating LUM/IVA treatment (See Section [11.5.6](#))

## 9 STUDY POPULATION

Eligibility will be reviewed and documented by an appropriately qualified member of the investigator's team before subjects are enrolled.

## 9.1 Inclusion Criteria

Subjects who meet all of the following inclusion criteria will be eligible.

1. Subject and/or legally appointed and authorized representative (e.g., parents or legal guardian) will sign and date an informed consent form (ICF) and where appropriate, an assent form.

2. Subject and/or legally appointed and authorized representative (e.g., parent or legal guardian) is willing and able to comply with scheduled visits, treatment plan, study restrictions, laboratory tests, contraceptive guidelines, and other study procedures.
3. Confirmed diagnosis of CF and homozygous for the *F508del-CFTR* mutation at Screening.
4. Subjects (male and female) will be aged 16 years and older on the date of informed consent or, where appropriate, assent.
5.  $\text{FEV}_1 \geq 40\%$  of predicted normal for age, sex, and height at Screening.

## 9.2 Exclusion Criteria

Subjects who meet any of the following exclusion criteria will **not** be eligible.

1. History of any illness or any clinical condition that, in the opinion of the investigator, might confound the results of the study or pose an additional risk in administering LUM/IVA to the subject, e.g., history of advanced liver disease.
2. Presence of moderate or severe hepatic impairment (Child-Pugh Class B or C).
3. Subjects currently receiving invasive mechanical ventilation.
4. Known history of alcohol or drug abuse in the past year, including but not limited to cannabis, cocaine, and opiates, as deemed by the investigator.
5. Any of the following abnormal laboratory values during screening:
  - o Alanine aminotransferase (ALT) or aspartate aminotransferase (AST)  $>5 \times \text{ULN}$
  - o ALT or AST  $>3 \times \text{ULN}$  with total bilirubin  $>2 \times \text{ULN}$
  - o Glomerular filtration rate  $\leq 30 \text{ mL/min/1.73 m}^2$ . This will be calculated by the Modification of Diet in Renal Disease study equation for subjects  $\geq 18$  years of age and calculated by the Counahan-Barratt equation for subjects aged 12 to 17 years.
6. Pregnant or nursing females (females of childbearing potential must have a negative pregnancy test at screening and Day 1).
7. Female subjects and female partners of male subjects who plan to become pregnant during Treatment Period or within 90 days following the last dose of LUM/IVA.
8. Sexually active subjects of reproductive potential who are not willing to follow the contraception requirements outlined in Section 11.5.7.1.
9. History of solid organ or hematological transplantation.
10. Ongoing or prior participation in an investigational drug study (including studies investigating LUM and/or IVA) within 30 days of screening
  - A washout period of 5 terminal half-lives of the previous investigational LUM/IVA or 30 days, whichever is longer
  - The duration of the elapsed time may be longer if required by local regulations.
11. Current use of commercial LUM/IVA combination therapy.

12. Subject, or close relative of the subject, is the investigator or a subinvestigator, research assistant, pharmacist, study coordinator, or other staff directly involved with the conduct of the study at that site.

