h Blood samples will be collected for clinical laboratory assessments ([Section 11.5.2](#)).

i Liver function testing (alanine aminotransferase [ALT], aspartate aminotransferase [AST], gamma-glutamyl transpeptidase [GGT], alkaline phosphatase [ALP], and total bilirubin) must be performed at the scheduled visits ([Section 11.5.2](#)).

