**Table 11-1 Safety Laboratory Test Panels**

Serum Chemistry	Hematology
Total Bilirubin, direct bilirubin	Hemoglobin
Alkaline phosphatase	Erythrocytes:
Aspartate aminotransferase	Mean corpuscular hemoglobin
Alanine aminotransferase	Mean corpuscular hemoglobin concentration
Gamma-glutamyl transferase	Mean corpuscular volume
	Platelets
	Reticulocytes (absolute)
	Leukocytes
	Differential (absolute and percent):
	Eosinophils
	Basophils
	Neutrophils
	Lymphocytes
	Monocytes

**Pregnancy ( $\beta$ -human chorionic gonadotropin) Tests for Females of Childbearing Potential:** Serum (Screening only) and urine pregnancy tests will be performed at the site as specified in [Table 3-1](#) and [Table 3-2](#). The serum and urine pregnancy tests will be analyzed at the central laboratory. The urine pregnancy test on Day 1 must be negative before the first dose of LUM/IVA. Additional urine pregnancy tests may be required according to local regulations and/or requirements

If a urine pregnancy test is positive, all LUM/IVA dosing will stop and the pregnancy will be confirmed with a serum  $\beta$ -human chorionic gonadotropin test. If confirmed, the pregnancy will be reported and the subject will be permanently withdrawn from LUM/IVA (Section 11.5.7.2). If a pregnancy test is positive, the procedures outlined in Section 11.5.7.2 will be followed.

**Follicle-stimulating hormone (FSH) (Screening Period only):** Blood sample for FSH will be measured for any suspected postmenopausal female with at least 12 months of continuous

spontaneous amenorrhea. Serum FSH levels must be within the postmenopausal reference range of the performing laboratory to be considered postmenopausal.

CFTR genotype (Screening Period only): *CFTR* genotyping will be performed to confirm the subject is homozygous for the *F508del-CFTR* mutation as documented in the subject's medical record. The results of the genotype must be obtained and reviewed during the Screening Period. CF genotyping can be waived if the subject has a documented genotype result from a previous Vertex study with a Screening Visit date of 01 June 2010 or later. Specific instructions will be provided in the Laboratory Manual.

Additional Evaluations: Additional clinical laboratory evaluations will be performed at other times if judged to be clinically appropriate.

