For purposes of study conduct, only laboratory tests done in the central laboratory may be used. Local laboratories may be used at the discretion of the local investigator for management of urgent medical issues. If a local laboratory test value is found to be abnormal and clinically significant, it will be verified by the central laboratory as soon as possible after the investigator becomes aware of the abnormal result. If it is not possible to send a timely specimen to the central laboratory (e.g., the subject was hospitalized elsewhere), the investigator may base the assessment of an AE on the local laboratory value.

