### **11.5.3 Liver Function Test Parameters**

#### Mandatory Liver Function Testing

Liver function testing (ALT, AST, GGT, ALP, and total bilirubin) must be performed as noted in [Table 3-1](#) and [Table 3-2](#).

It is strongly recommended that subjects with new treatment-emergent ALT or AST elevations of  $>3 \times$  ULN, total bilirubin  $>2 \times$  ULN, or clinical symptoms be followed closely, including repeat confirmatory testing performed by the central laboratory within 48 to 72 hours of the initial finding and subsequent close monitoring of ALT, AST and bilirubin levels, as clinically indicated. If ALT or AST is  $>5 \times$  ULN, follow-up levels must be obtained within  $7 \pm 2$  days.

If a subject cannot return to the site for liver function testing, a local laboratory may be used. Elevations in LFTs at the local laboratory must be reported immediately to the medical monitor, and the subject must have the tests repeated and sent to the central laboratory as soon as possible (ideally within 48 to 72 hours).

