^h Blood samples will be collected for clinical laboratory assessments (Protocol Section 11.5.2).

ⁱ Liver function testing (alanine aminotransferase [ALT], aspartate aminotransferase [AST], gamma-glutamyl transpeptidase [GGT], alkaline phosphatase [ALP], and total bilirubin) must be performed at the scheduled visits (Protocol Section 11.5.2).

Table 11-2 Treatment Period and Safety Follow-up Visit Assessments – Study VX15-809-114

Event/Assessment	Day 1	Week 12	Week 24	Week 36	Week 48	Safety Follow-up Week 52 ^a
Clinic visit	X	X	X	X	X	X
Vital signs ^b	X	X	X	X	X	X
Physical examination ^c					X	X ^d
Liver Function Testing ^e	X	X	X	X	X	X
Urine pregnancy test (all female subjects of childbearing potential)	X	X	X	X	X	X
Randomization ^f	X					
Standardized education on adherence	X					
Concomitant medications, treatments, and procedures	X	X	X	X	X	X
Smart Adherence Technology-Reported Adherence ^g		X	X	X	X	

LUM/IVA drug count ⁱ		X	X	X	X	
Ophthalmologic examination ^j					X	
AEs and SAEs	Continuous from signing of ICF or assent (where applicable)					
LUM/IVA resupply	Every 3 months throughout study					

^a The Safety Follow-up Visit is 28 (\pm 7) days after the last dose of LUM/IVA (Protocol Section 8.1.3).

^b Vital signs will be assessed following a 5-minute rest in the seated or supine position.

^c Symptom-targeted PEs will occur at any time during the study if triggered by AEs or if deemed necessary by the investigator.

^d Required for subjects who do not begin commercial LUM/IVA after Week 48 only.

^e Day 1 only blood draws will be collected before the first dose of LUM/IVA. Liver function testing (alanine aminotransferase [ALT], aspartate aminotransferase [AST], gamma-glutamyl transpeptidase [GGT], alkaline phosphatase [ALP], and total bilirubin) must be performed at the scheduled visits (Protocol Section 11.5.2).

^f Randomization must occur after all inclusion and exclusion criteria are met and before the first dose of LUM/IVA. Randomization will be done through IWRS.

^g Data will be collected for all subjects throughout the study in real-time. Subjects in Study Arm A will review data with physicians at study visits.

ⁱ LUM/IVA drug count will be collected at the end of specified study visits.

^j See Protocol Section 11.5.6.

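### Exclusion criterion 5 needs a calculated GFR at screening, but no scheduled test measures serum creatinine

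*Protocol*

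**What the plan says.** Criterion 5 in Protocol Section 9.2 opens with "Any of the following abnormal laboratory values during screening" and gives three limits: ALT or AST above 5 × ULN; ALT or AST above 3 × ULN together with total bilirubin above 2 × ULN; and GFR at or below 30 mL/min/1.73 m². On the GFR it says: "This will be calculated by the Modification of Diet in Renal Disease study equation for subjects" aged 18 or over, and it names the Counahan-Barratt equation for ages 12 to 17.

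The screening tests are set out in Table 3-1. Its liver function footnote says "Liver function testing (alanine aminotransferase [ALT], aspartate aminotransferase [AST], gamma-glutamyl transpeptidase [GGT], alkaline phosphatase [ALP], and total bilirubin) must be performed" at the scheduled visits. The laboratory panels are defined in Table 11-1 (Section 11.5.2). The serum chemistry column there begins with "Total Bilirubin, direct bilirubin" and continues with alkaline phosphatase, AST, ALT and GGT. SAP Appendix A reproduces the screening schedule and, for hematology, points back to the same protocol section: "Blood samples will be collected for clinical laboratory assessments (Protocol Section 11.5.2").

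On the source of results, Section 11.5.2 says "For purposes of study conduct, only laboratory tests done in the central laboratory may be used".

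Section 9 requires eligibility to be reviewed and documented before enrolment. Footnote f of Table 3-2 allows randomisation only once every criterion has been met.

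**The concern.** The criterion applies to every subject and depends on a calculated laboratory value, yet the schedule and the panel that should supply the value do not include the analyte. Sites may handle this differently: some may order an extra test, some may rely on the history, and some may pass over the limit.

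The subject at stake is one with severe renal impairment that nobody has recognised, who could be randomised without the check the protocol intends. SAP Section 8.2.7 treats entry despite a violated criterion as a potential important protocol deviation, but without a GFR value such a violation could go unnoticed.

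**Working it through.** No arithmetic beyond counting applies. The check sets the criterion beside the tests that are scheduled.

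**1. What each limit needs, and what supplies it**

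| Limit in criterion 5 | Input | Scheduled at screening? |
|---|---|---|
| ALT or AST > 5 × ULN | ALT, AST | Yes, liver function testing |
| ALT or AST > 3 × ULN with total bilirubin > 2 × ULN | ALT, AST, total bilirubin | Yes, liver function testing |
| GFR ≤ 30 mL/min/1.73 m² | Serum creatinine (assumption: standard form of both equations) | No |

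Counahan-Barratt also uses height, which Table 3-1 does collect. Creatinine is the missing input. Two of the three limits are supplied, and 3 − 2 = 1 is not.

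**2. Where creatinine could have been listed**

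- Protocol Table 3-1 has 15 rows. Four are laboratory rows: serum pregnancy test, serum FSH, hematology and liver function testing. (Genotyping is done only if undocumented.) Renal tests: 0 of 4.
- The screening table in SAP Appendix A has the same 15 rows and the same four laboratory rows. Renal tests: 0 of 4.
- The serum chemistry column of Protocol Table 11-1 lists total bilirubin, direct bilirubin, alkaline phosphatase, AST, ALT and GGT, all hepatic. Renal tests: 0 of 6.
- Day 1 in Table 3-2 has only liver function testing and a urine pregnancy test as laboratory work.

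Section 11.5.2 is where such a test would be expected. It already specifies tests done only at screening (serum pregnancy, FSH, CFTR genotype).

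**3. Could redaction explain the gap?**

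No. The Table 3-1 footnotes run from a to i without a break, and the table's only redaction is in its abbreviation list. Table 11-1 shows none. Table 3-2 lacks a footnote h, but that falls between the adherence and drug-count rows of the treatment period, so it cannot conceal a screening test.

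**4. Other routes to a value**

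- *Local laboratory.* Section 11.5.2 says "Local laboratories may be used at the discretion of the local investigator for management of urgent medical issues", and Section 11.5.3 says "If a subject cannot return to the site for liver function testing, a local laboratory may be used". Neither exception covers a screening GFR.
- *Unscheduled central test.* This would comply. Section 11.5.2 allows extra evaluations where clinically appropriate, but that is left to judgement, and no schedule row or panel entry asks for the test.
- *Data from another study of the sponsor.* Section 8.1.1 allows reuse of screening data obtained within 28 days before dosing. This covers some subjects only, and the documents do not say that those data include creatinine.

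**The case against.** The strongest reply has four parts.

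- **The text already obliges sites to obtain a GFR.** Criterion 5 gives the limit and the equations, eligibility must be documented, and randomisation must wait. A careful site would order a central creatinine. This is true, and it is why inconsistent practice is a risk and not a certainty. But the plan then relies on each site noticing that its schedule is incomplete.
- **Creatinine may have been measured in practice.** SAP Section 8.4.2 lists abnormal chemistry results separately from abnormal liver function results, although direct bilirubin is the only analyte that Table 11-1 adds to the liver function set. That may hint at a wider central panel. However, Section 8.4.2 names no renal analyte, and SAP Section 8.4 describes the laboratory values as liver function tests. The Laboratory Manual is not available, and the passage that mentions it concerns genotyping. What is established is that the protocol and SAP do not schedule creatinine, not that no one measured it.
- **The consequence is small.** Known renal disease can be picked up from the medical history (Section 11.2) or by investigator judgement under criterion 1. The documents describe no specific LUM/IVA risk at this GFR. Both points stand, and they limit the weight of the finding.
- **The study was terminated early (SAP Section 3).** A new screening test can no longer change its conduct. That narrows what can be done for this trial, but it does not make the protocol consistent.

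**Conclusion.** The concern holds. One of the three limits in criterion 5 has no scheduled input: 0 of 4 laboratory rows in the protocol's screening schedule, 0 of the same 4 in the SAP copy, and 0 of 6 serum chemistry analytes in Table 11-1 are renal. Following the schedule and panel exactly leaves a mandatory exclusion that cannot be assessed.

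These figures count tests, not subjects at risk. The documents do not say how many subjects would have a GFR at or below 30. The conclusion rests on the assumption that both equations need serum creatinine, and the judgement of modest impact rests on the assumption that few subjects would be affected. The adherence endpoints and the power are not affected. The inconsistency should be corrected, but it does not threaten the results.

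**What to change.** Add serum creatinine to the serum chemistry panel in Protocol Table 11-1 and to the screening blood draw in Table 3-1, carry the change into SAP Appendix A, and require GFR to be calculated before randomisation. The cost is one more analyte on a central blood draw already taken at screening, with no extra visit.

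If renal screening is not wanted, delete the GFR bullet or replace it with an exclusion based on history. That costs one edited bullet.

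Because the study has stopped, the practical step for subjects already enrolled is to check whether a GFR was documented. The schedule correction matters if the protocol text is used again.
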